## 6.4. SUBJECT DIARY CARD

Subjects will be given diary cards from Visit 2 until Follow-up Visit 1 to record the following:

- From Day 1 until the last visit of the treatment period, subjects will be asked to record the date of IMP intake, the number of tablets taken for each administration, any change in intake and reason for the change, and monthly urine pregnancy test outcome (only for WOCBP, see Section 4.5.3.1.1).
- From Day 1 until Follow-up Visit 2, subjects will be asked to record changes in concomitant medication regimen, including new medicines not captured in medication history, and any other concomitant medication used as well as any emerging AE.

Subjects will be instructed to bring their diary cards and used/unused IMP to each clinical study center visit. At each clinical study center visit, review of compliance with the diary cards and subject re-training if needed, will be performed.

## 6.5. EFFICACY ASSESSMENTS

### 6.5.1. Modified Rodnan Skin Score

mRSS is an established primary outcome measure in most therapeutic studies in systemic sclerosis, based on the evidence that skin thickness serves as a surrogate for overall disease activity, severity, and mortality in systemic sclerosis. mRSS scoring will be performed at Visit 1 (screening), Visit 2 (baseline), Visits 4, 5, 7, and 9, ED (if applicable), and Follow-up Visit 1. mRSS will be assessed in a standardized manner according to published protocols by the SCTC and the World Scleroderma Foundation (Khanna D. et al., 2017) by the responsible study physician. Preferably, each subject will be assessed by the same study physician (or nurse practitioner, as acceptable according to local clinical study center setup and meeting the experience criterion defined outside the protocol) for the entire study. The 17-site mRSS will be used, with each site assessed on a scale of 0 to 3 with a maximum score of 51. For individual subjects, clinically meaningful changes in skin score (MCID) are 4.7 skin score units and/or at least 20% change in overall mRSS (Khanna D. et al., 2006). Regardless of experience, each assessor will need to undergo study-specific training and qualification to ensure consistency. In the event of a change of assessor, consistency of scoring between assessors should ideally be assessed and documented (i.e. new and previous assessor carry out scoring in parallel).

## 6.6. SAFETY ASSESSMENTS

This section describes methods and timing for all safety assessments and recording. Additional assessments (e.g. unscheduled clinical laboratory tests or extra vital signs recordings) are allowed to ensure appropriate collection of safety data and to assess any perceived safety concerns.

**For subjects who, due to any COVID-19-related reason, cannot perform the study procedures.**

If Visit 9 needs to be postponed until after Week 24, regular phone calls at Week 24 and every 14 days thereafter should be implemented to evaluate the subject's safety until a visit can take place on-site. In addition, if any of the follow-up visits cannot be performed on site, a phone call to evaluate the subject's safety should be performed.

During these phone calls, the investigator should at least discuss the following items and collect the following information as much as possible:

- subject's general condition and ongoing study medication intake
- information on any adverse events (changes of ongoing or new events)
- information on concomitant medication intake
- completion of subject diary cards and urine pregnancy test and result (monthly, if applicable) by the subject
- the possibility for local laboratory testing, vital signs, and ECG should be considered, and discussed. This local testing may occur either prior to the phone call, or as a consequence of the exchanged information, at the discretion of the investigator.

All adverse events including those based on, or identified by local testing need to be reported in the eCRF, and any SAEs should be reported within 24 hours with the SAE form.

Urine pregnancy tests to perform the monthly pregnancy test at home until follow-up visit 1 (if applicable) and treatment or follow-up diary cards will also be shipped to the patient to cover the longer period between on-site visits.

### 6.6.1. Adverse Events

The AEs reporting period for safety surveillance begins when the subject signs the ICF and ends at his/her last follow-up visit as defined in the Schedule of Activities (see Section 6.11).

Detailed definitions, ratings, and reporting requirements for AEs and SAEs are found in Section 9.

### 6.6.2. Clinical Laboratory Evaluations

The following clinical laboratory safety tests will be performed:

- Hematology: hematocrit, mean corpuscular volume, mean corpuscular hemoglobin, mean corpuscular hemoglobin concentration, hemoglobin, red blood cell count, white blood cell count, white blood cell differential count (absolute and relative), and platelets.
- Coagulation: INR, thromboplastin time, and partial thromboplastin time.
- Serum/plasma chemistry: random glucose, urea, creatinine, uric acid, sodium, potassium, calcium, chloride, phosphorus, AST, ALT, GGT, total bilirubin, alkaline phosphatase,

lactate dehydrogenase, total serum bile acid, albumin, total proteins, triglycerides, cholesterol (total, low density lipoprotein, and high density lipoprotein), creatine kinase, and C-reactive protein.

- Urinalysis:
  - Dipstick: pH, glucose, proteins, blood, leucocytes, ketones.
  - Microscopic examination of the sediment (cylinders, erythrocytes, leucocytes) if indicated.
- Serology: hepatitis B surface antigen, hepatitis C virus antibody, and HIV-1 and HIV-2 antibodies (only at screening). Positive hepatitis and HIV results should be reported by the investigator as required by local law.
- FSH test for females at screening to confirm menopause if applicable.
- Pregnancy test for females: serum beta human chorionic gonadotropin at screening, urine pregnancy test on a monthly basis (only for WOCBP).

The clinical laboratory evaluations will be performed at visits specified in the Schedule of Activities in Section 6.11 (see also Section 6.1, “[Timing of Assessments](#)”). Reference ranges will be supplied by the central laboratory. Clinical laboratory values outside the normal range will be flagged and clinical relevance will be assessed by the investigator. Only laboratory test abnormalities judged as clinically significant by the principal investigator should be recorded as AEs.

The details of blood and urine sample handling and shipment instructions will be provided in a separate laboratory manual.

### 6.6.3. Physical Examination

Physical examinations will be conducted by a physician, trained physician’s assistant, or nurse practitioner (as acceptable according to local regulation) at visits specified in the Schedule of Activities in Section 6.11. The person conducting the physical examination will document this in the subject’s medical records. Clinically significant abnormal findings should be recorded as AEs. Height and weight will only be recorded at screening.

### 6.6.4. Vital Signs

Vital signs (SBP, DBP, heart rate, respiratory rate, and body temperature) will be recorded in a standardized manner (i.e. after the subject has rested in a supine position for 5 minutes) at visits specified in the Schedule of Activities in Section 6.11. Clinically significant abnormal values should be recorded as AEs.

### 6.6.5. 12-lead Electrocardiogram

At the time points specified in the Schedule of Activities (see Section 6.11) a 12-lead ECG will be recorded and results will be sent for central reading. Triplicate ECGs will be performed irrespective of IMP intake at Visit 1 (screening), within 30 minutes before IMP intake and between 2 to 3 hours after IMP intake at Visit 2 (baseline) and Visit 3. A single ECG will be performed within 30 minutes before IMP intake at Visits 7 and 9, and irrespective of IMP intake at ED (if applicable) and Follow-up Visit 1. The ECG must be taken after subjects rested for at least 5 minutes in the supine position. In case an indwelling catheter is used, ECGs may be recorded after blood sampling, provided that there is at least 30 minutes between catheter insertion and the ECG recording. When catheter insertion would fail, the 12-lead ECG needs to

be taken before the venipuncture and at least 30 minutes after the failed attempt. Triplicate ECGs will be performed preferably within a time span of 6 minutes, with an approximate 2-minute interval between ECGs. Parameters to be recorded include the following: heart rate, PR interval, QRS interval, uncorrected QT interval, morphology, and rhythm analysis. QTcF will be considered as normal if  $\leq 450$  ms, while a prolongation of QTcF to  $\geq 500$  ms or an increase from baseline  $>60$  ms will be considered a threshold of concern. Immediately after recording, the ECG will be reviewed by the investigator on clinically significant abnormalities. This immediate review during the visit needs to be documented in the subject's source. After receipt of the central report, also all flagged ECG abnormalities need to be assessed by the investigator on clinical relevance. Clinically significant abnormal values should be recorded as AEs.

[REDACTED]

[REDACTED]

[REDACTED]

[REDACTED]

[REDACTED]

[REDACTED]

[REDACTED]

[REDACTED]

[REDACTED]

[REDACTED]

[REDACTED]

[REDACTED]

[REDACTED]

[REDACTED]

[REDACTED]

[REDACTED]

## 6.9. OTHER ASSESSMENTS

[REDACTED]

[REDACTED]

[REDACTED]

[REDACTED]

[REDACTED]

[REDACTED]

[REDACTED]

[REDACTED]

[REDACTED]

[REDACTED]

[REDACTED]

[REDACTED]

[REDACTED]

[REDACTED]

[REDACTED]

[REDACTED]

[REDACTED]

[REDACTED]

[REDACTED]

[REDACTED]

[REDACTED]

[REDACTED]

[REDACTED]

[REDACTED]

[REDACTED]

[REDACTED]

[REDACTED]

## 6.10. SAMPLE MANAGEMENT

### **Blood and Urine Samples for Routine Safety Tests, Serology, FSH, and Pregnancy Tests**

All blood and urine samples for routine safety tests, serology, FSH, and pregnancy test will be analyzed in a central laboratory and will be destroyed after analysis.

### **Blood Samples for [REDACTED]**

After the EoS (e.g. Last Subject Last Visit), all biological samples obtained during the clinical study may be stored for a period of maximum 5 years, after which the samples will be destroyed. The sample storage period will be in accordance with the IEC/IRB-approved ICF and applicable laws (e.g. health authority requirements).

The stored samples shall only be used by the sponsor, sponsor partners and/or other companies contracted by the sponsor, for research related to this clinical study. Any research outside the context described in this CSP may only be conducted after approval by the IEC/IRB and Regulatory Authority and after obtaining informed consent from the subject.

[figure not shown]
If research is performed on genetic material of the samples, then this can only be performed in context of the described CSP [REDACTED] and the data obtained may in no case be used for the purpose of identification or re-identification of subjects.

## 6.11. SCHEDULE OF ACTIVITIES

For detailed instructions on the clinical study procedures, please see referred Sections and Section 6.1, “Timing of Assessments”.

EVENT	SCREENING	TREATMENT PERIOD									FOLLOW-UP j	
	1	2	3	4	5	6	7	8	9	ED a	FU1	FU2
Study Day (D) or Week (W) b ± days (d)	D-28 to D-1	D1	W2 ±2d	W4 ±2d	W8 ±4d	W12 c ±4d	W16 ±4d	W20 c ±4d	W24 i ±4d		W28 ±7d	W36 ±7d
Informed consent (Section 6.3)	✓											
Inclusion/exclusion criteria (Section 6.3)	✓	✓										
Demographics (Section 6.3)	✓											
Medical history/concurrent illnesses (Section 6.3)	✓											
FSH test (Section 6.6.2)	✓											
Randomization (Section 4.6.1)		✓										
Phone call						✓		✓				
Pregnancy test d (Section 6.6.2)	✓	✓		✓	✓	✓	✓	✓	✓	✓	✓	
Physical examination (Section 6.6.3)	✓	✓	✓	✓	✓		✓		✓	✓	✓	
Vital signs (Section 6.6.4)	✓	✓	✓	✓	✓		✓		✓	✓	✓	
12-Lead ECG e (Section 6.6.5)	✓	✓	✓				✓		✓	✓	✓	
Serology (Section 6.6.2)	✓											
Clinical laboratory tests (Section 6.6.2)	✓	✓	✓	✓	✓		✓		✓	✓	✓	

EVENT	SCREENING	TREATMENT PERIOD									FOLLOW-UP j	
		1	2	3	4	5	6	7	8	9	ED a	FU1
Study Visit	1	2	3	4	5	6	7	8	9	ED a	FU1	FU2
Study Day (D) or Week (W) b ± days (d)	D-28 to D-1	D1	W2 ±2d	W4 ±2d	W8 ±4d	W12 c ±4d	W16 ±4d	W20 c ±4d	W24 i ±4d		W28 ±7d	W36 ±7d
mRSS (Section 6.5.1)	✓	✓		✓	✓		✓		✓	✓	✓	

Dispense subject diary		✓	✓	✓	✓		✓		✓	✓	✓	
Collect subject diary			✓	✓	✓		✓		✓	✓	✓	✓
Dispense IMP		✓	✓	✓	✓		✓					
Review IMP compliance			✓	✓	✓		✓		✓	✓		

EVENT	SCREENING	TREATMENT PERIOD									FOLLOW-UP j	
		1	2	3	4	5	6	7	8	9	ED a	FU1
Study Visit	1	2	3	4	5	6	7	8	9	ED a	FU1	FU2
Study Day (D) or Week (W) b ± days (d)	D-28 to D-1	D1	W2 ±2d	W4 ±2d	W8 ±4d	W12 c ±4d	W16 ±4d	W20 c ±4d	W24 i ±4d		W28 ±7d	W36 ±7d
Dose IMP (Section 5.2)		q.d. throughout the treatment period										
AE assessment (Section 6.6.1)	Throughout the study											
Concomitant medication assessment and documentation (Section 4.5.3.2)	Throughout the study											

FU=follow-up, QoL=quality of life.

a ED visit if applicable.

b Week is defined as 7 days.

c This will be a phone call to assess safety (no clinical study center visit).

d Serum pregnancy test at screening, urine pregnancy test at all other visits.

e Triplicate ECGs will be performed irrespective of IMP intake at Visit 1 (screening), within 30 minutes before IMP intake and between 2 to 3 hours after IMP intake at Visit 2 (baseline) and Visit 3. A single ECG will be performed within 30 minutes before IMP intake at Visits 7 and 9, and irrespective of IMP intake at ED (if applicable) and Follow-up Visit 1.

i If Visit 9 (Week 24) cannot be conducted within the time window of ±4 days, the visit window can be extended to ±28 days (i.e. can be extended or shortened up to 28 days) to enable conduct of the visit on site. If Visit 9 is conducted after Week 24, additional regular phone calls at Week 24 and every 14 days thereafter should be implemented, until an on-site Visit 9 can take place, or until Week 32, to evaluate the subject's safety. In addition, if any of the follow-up visits cannot be performed on-site, a phone call to evaluate the subject's safety should be performed on the date of the visit. The information to be collected during these phone calls is detailed in Section 6.6.

j The FU visits need to be scheduled in relation to the last dose of IMP. FU1 should be 28 days ±7 days after the last IMP administration, and FU2 should be 84 days ±7 days after the last IMP administration.

## **7. STATISTICAL METHODS**

All statistical methods shall be detailed in a statistical analysis plan (SAP) that will be prepared before the Week 24 primary analysis. All relevant data collected in this clinical study will be documented using summary tables, figures, and subject data listings.

Any deviations from the protocol are to be justified in the SAP.

### **7.1. DETERMINATION OF SAMPLE SIZE**

Sample size was based on empirical considerations. The number of subjects (30) included in this study should give reasonable precision around the estimates derived for the efficacy evaluation.

The primary endpoint of the study is the change from baseline in mRSS over 24 weeks.

Considering 20 and 10 subjects in the GLPG1690 and placebo arm, respectively, and a common standard deviation of 5 on the change from baseline in mRSS, the MCID of 4.7, and taking into account a 10% dropout, the probability to observe a treatment effect of more than 4 points is 63%.

### **7.2. POPULATION FOR ANALYSES**

#### **7.2.1. All Screened Subjects**

All subjects who signed and dated an ICF and underwent screening assessments to check whether or not they are eligible to participate in the clinical study.

#### **7.2.2. All Enrolled Subjects**

All subjects who were found eligible to participate in the clinical study and could be randomized.

#### **7.2.3. All Randomized Subjects**

All enrolled subjects who were randomized into the clinical study.

#### **7.2.4. Full Analysis Set**

All randomized subjects who have received/used at least 1 dose of IMP.

#### **7.2.5. Per-Protocol Set**

All Full Analysis Set subjects who did not have a major protocol deviation that impacts the efficacy results (as defined in a protocol deviation plan). The determination of the per-protocol population will be finalized and documented prior to database lock and unblinding.

### 7.2.6. Safety Analysis Set

All randomized subjects who used at least 1 dose of IMP.

[REDACTED]

[REDACTED]

[REDACTED]

[REDACTED]

[REDACTED]

[REDACTED]

## 7.3. STATISTICAL ANALYSES

### 7.3.1. General Statistical Considerations

Summary tabulations will be presented and will display the number of observations, mean, standard deviations and/or standard error, as appropriate, median, minimum, and maximum for continuous variables, and the number and percentage per category for categorical data. In addition to tabulated descriptive statistics, graphical data displays may be used to summarize the data. Unless otherwise noted, inferential statistics will be interpreted at the 2-sided 5% significance level. Data may be pooled across centers and countries.

### 7.3.2. Primary Analysis

The primary analysis will be performed when all subjects have completed the Week 24 visit (or discontinued earlier). Every effort will be made to keep the subjects and investigators blinded to individual treatment assignments until completion of the final analysis (after the last subject has completed the last follow-up visit in this study).

### 7.3.3. Interim Analysis

No interim analysis is planned for the study.

### 7.3.4. Analyses of Demographics and Baseline Characteristics

Subject disposition (including reasons for early discontinuation), protocol deviations, demographics, baseline characteristics, medical history, and concomitant medications will be analyzed descriptively and/or listed for the Full Analysis Set (Section 7.2.4).

### 7.3.5. Analyses of Efficacy Parameters

All efficacy parameters will be analyzed descriptively in the Full Analysis Set (Section 7.2.4) unless otherwise specified.

#### 7.3.5.1. Analysis for Primary Efficacy Endpoint

Change from baseline in mRSS will be presented descriptively and graphically over time by treatment group.

Change from baseline in mRSS will be analyzed using a mixed-effects model for repeated measures (MMRM). The model will include treatment and visit as fixed effects, baseline mRSS and country as covariates, and treatment-visit as interaction terms. Least square (LS) means with 95% confidence intervals (CIs) will be calculated from the model at each time point as well as difference from placebo in LS means with 95% CIs.

The number and percentage of subjects with a clinically meaningful change in skin score (as defined in Section 6.5.1) will be summarized by treatment.

Change from baseline in mRSS will also be analyzed for a series of subgroups (such as baseline characteristics and background treatment). Details will be provided in the SAP.

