### Open-label Extension

Subjects who completed the Week 24 visit will be offered treatment with GLPG1690 in an optional open-label extension, provided regulatory and Independent Ethics Committee (IEC)/Institutional Review Board (IRB) approvals for such an extension is granted. In this case, the follow-up visits are not performed for these subjects. This extension is described in a separate protocol, Study GLPG1690-CL-206.

For the rollover of a subject into the GLPG1690-CL-206 study, a complete rollover visit, at Visit 9 of this study (GLPG1690-CL-204), is required.

If Visit 9 cannot be conducted on site within the extended window of Week 24 +28 days, due to any COVID-19-related reason, the subject will be given the opportunity to complete an on-site visit and rollover into the Open-Label Extension study until Week 32. The Visit 9/rollover assessments should be performed at this on-site visit, [REDACTED]. The subject will however be off study medication and not receive IMP between Week 28 to 32. If the subject decides not to rollover to GLPG1690-CL-206, and the on-site visit can be conducted in the window Week 32 ±7 days after initial IMP start in GLPG1690-CL-204, the on-site visit should be considered to be Follow-up visit 1.

If the rollover visit cannot be scheduled before Week 32, the subject will continue in the follow-up period of GLPG1690-CL-204 with a first follow-up visit 4 weeks after last IMP administration.

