### 4.2.2. Clinical Study Design Rationale

This is a randomized, double-blind, parallel-group, placebo-controlled, multi-center, Phase 2a 24-week study in subjects with systemic sclerosis. The randomized double-blind study design was chosen because it is the most rigorous method to generate high-quality scientific data and there is no approved alternative treatment available for comparison. A placebo-controlled study contains internal evidence of assay sensitivity (i.e. when a difference is demonstrated, it is interpretable without reference to external findings), measures absolute safety and efficacy (i.e. it measures the total pharmacologically mediated effect of treatment), is very efficient (i.e. can measure treatment effects with a smaller sample size compared with any other type of controlled study) and minimizes the effect of subject and investigator expectations (ICH E10, 2000). The 2:1 randomization to GLPG1690 avoids unnecessary exposure of subjects to placebo and is typical for Phase 2a studies in systemic sclerosis. The subject eligibility criteria are typical for patient studies in early progressive diffuse cutaneous systemic sclerosis. Based on current European League Against Rheumatism (EULAR) and Scleroderma Clinical Trials Consortium (SCTC) recommendations, background treatment is allowed as defined in Section 4.5.3.2, "Prior and Concomitant Medications". The study duration (24 weeks) was chosen based on experience with previous clinical studies in diffuse systemic sclerosis with a similar mode of action and similar clinical endpoints. The 12-week follow-up period was chosen based on experience with a previous clinical study targeting LPA1 in order to assess the occurrence of flares after IMP discontinuation in subjects with systemic sclerosis compared to placebo.

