#### 5.3.2.3. Analysis Methods

The following analyses will be done on the FAS as the primary analysis, and repeated on the PP Analysis Set, if more than 10% of the subjects have at least one major protocol deviation, to confirm the results of the primary analysis:

The mRSS and change from baseline in mRSS score (primary endpoint) will be summarized by descriptive statistics. Mean ( $\pm$ SE) plots over time (analysis visits based on time window) for both treatment groups, and similar mean ( $\pm$ SE) plots for the change from baseline will be presented. Additionally, spaghetti plot of change from baseline will be displayed with subjects presented by treatment.

Change from baseline in mRSS will be analyzed using a mixed-effects model for repeated measures (MMRM). The model will include treatment and visit as fixed effects, baseline mRSS and country as covariates, and treatment-visit as interaction terms. Subject will be included in the model as a random effect. The likelihood-based MMRM will be performed using a SAS PROC MIXED procedure (see [Appendix 3](#)), and the Kenward-Roger method for degrees of freedom will be applied. The restricted maximum likelihood (REML) method will be used for estimation. The Least Square (LS) means along with the associated SE and 95% CIs, as well as the difference in LS means and associated 95% CIs will be displayed at each time point. For exploratory purpose only, p-values will also be displayed for testing the difference in LS means at each timepoint. The p-value derived for the overall difference between treatment groups will also be displayed, as well as all p-values for fixed effects included in the model.

The variance-covariance matrix will be assumed to be unstructured. If the procedure does not converge then a compound symmetric variance-covariance matrix will be used instead.

The number and percentage of subjects with a clinically meaningful change in skin score (as defined in section 5.3.2.2) will be summarized by treatment. Incidence will be derived overall (at any post-baseline timepoint) and for each analysis visit.

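### At the final analysis the mRSS by-visit means appear to run on to a Week 28 visit scored in different subjects, and the readable plan has no paired off-drug summary to tell change from composition

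*Protocol*

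**What the plan says.** Protocol 7.3.5.1 states "Change from baseline in mRSS will be presented descriptively and graphically over time by treatment group" and gives no last visit. SAP 5.3.2.3 plans mean (±SE) "plots over time (analysis visits based on time window) for both treatment groups", a spaghetti plot of individual changes from baseline, and responder incidence both per analysis visit and at any visit after baseline. SAP Table 2 gives mRSS a Week 24 window of Days 142–197 and a Week 28 window from Day 198 with no upper limit. SAP 3.3.4 keeps the value closest to the target day in each window and only lists the others.

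mRSS is scored at Visit 9, at early discontinuation (ED) and at Follow-up Visit 1 (FU1), but not at Follow-up Visit 2 (Protocol 6.5.1 and 6.11). FU1 is thus the only scheduled post-treatment score. For subjects who enter the extension, Protocol 4.1 says: "In this case, the follow-up visits are not performed for these subjects". The same section lets a subject delayed by COVID-19 have the Visit 9/rollover assessments off IMP up to Week 32 and then enter the extension.

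Protocol 4.2.2 explains that the 12-week follow-up was chosen "to assess the occurrence of flares after IMP discontinuation in subjects with systemic sclerosis compared to placebo". SAP section 4 limits the primary-analysis output to data up to the Week 24 visit, with a later final analysis once follow-up is complete.

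**The concern.** On a mean-by-visit plot the eye reads the segment from Week 24 to Week 28 as what happened when drug was stopped. Here that segment joins a mean over nearly everyone still in the study to a mean over a self-selected remainder. Entry to the extension is optional and is offered to those who complete the Week 24 visit, so the choice can be made with the skin response known. If subjects who decline had a worse Week 24 response than those who accept, the line rises with nobody worsening. If they had a better response, a real worsening can be hidden. The tendency may differ between arms.

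This matters because worsening after withdrawal, compared with placebo, is the stated reason for the follow-up period, and FU1 is the only scheduled mRSS that bears on it. Read literally, the responder incidence at any visit after baseline also gives subjects with a Week 28 score one more chance to count as responders.

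**Working it through.** 1. **The plan's own figure, for scale.** The inputs in Protocol 7.1 are 20 subjects on GLPG1690 and 10 on placebo, SD 5 for the mRSS change, and a true effect equal to the MCID, 4.7. The result given there is: "taking into account a 10% dropout, the probability to observe a treatment effect of more than 4 points is 63" per cent. With 10% dropout, 20 × 0.9 = 18 and 10 × 0.9 = 9. SE = 5 × √(1/18 + 1/9) = 2.041. P(observed > 4) = Φ((4.7 − 4)/2.041) = Φ(0.343) = 63.4%, so the figure reproduces. It does not bear on Week 28. It supplies the yardsticks: SD 5, effect of interest 4 points, MCID 4.7, and 18 + 9 completers.

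2. **Which FU1 scores reach the Week 28 column.** FU1 is due 28 ± 7 days after the last dose. With the last dose on Day 169, that is Days 190–204. Days 190–197, which are 8 of the 15 allowed days and include the nominal Day 197, fall in the Week 24 window. There a Visit 9 score near Day 169 is closer to target, so the FU1 score is only listed. If no closer score exists, FU1 serves as Week 24. With the last dose on Day 165, 12 of 15 days fall in the Week 24 window; on Day 173, 4 of 15.

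3. **Who else reaches it.** The Week 24 window ends at 169 + 28 = Day 197. A COVID-19-delayed rollover visit after that day, up to Week 32 (Day 225), falls in the Week 28 window, although the subject then enters the extension. The column is therefore selected by rollover and by visit day.

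4. **Size of the composition step.** The documents give no rollover rate, so the inputs below are assumptions. Let p be the share rolling over, and let R and N be the Week 24 means of rollover and non-rollover subjects. The Week 24 mean is pR + (1 − p)N. With no true change, the mean of those left at FU1 is N. Step = N − [pR + (1 − p)N] = p(N − R).

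| p | Step if the difference is 2 | Step if the difference is 5 | Subjects left for FU1 (GLPG1690 + placebo) |
|---|---|---|---|
| 50% | 1.0 | 2.5 | 9.0 + 4.5 |
| 60% | 1.2 | 3.0 | 7.2 + 3.6 |
| 70% | 1.4 | 3.5 | 5.4 + 2.7 |
| 80% | 1.6 | 4.0 | 3.6 + 1.8 |

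The sign follows the sign of N − R, and the step is zero if N = R. The table describes subjects eligible for FU1. After steps 2 and 3, the Week 28 column can hold fewer or other subjects.

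5. **A second model.** Let non-rollover subjects be the upper tail of a latent variable with correlation ρ to the Week 24 change (SD 5). The expected step is 5ρφ(c)/(1 − p), with c = Φ⁻¹(p). For ρ from 0.3 to 0.8 this gives 1.2–3.2 points at p = 50% and 1.7–4.6 at p = 70%. A simulation at p = 70% (5 of 18 and 3 of 9 remaining), with ρ = −0.5 and a true worsening of +2, showed unpaired steps of −0.9 (GLPG1690) and −0.5 (placebo): the worsening was hidden.

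6. **What pairing does.** In that simulation the paired change returned +2.0, but each Week 28 score was set to the Week 24 score plus a constant, so exact recovery was built in. If selection acts on the observed Week 24 score and the Week 24–Week 28 correlation is r, a residual of (1 − r) × shift remains, in the opposite direction. With an assumed r = 0.8 and a shift of 2.9, that is 0.2 × 2.9 ≈ 0.6 points.

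**The case against.** The endpoint is defined over the treatment period (SAP 2.2), subgroup summaries are over 24 weeks (SAP 5.3.5), and primary-analysis output stops at Week 24. This stands. Extension to Week 28 is inferred from Table 2 together with 5.3.2.3, and it concerns only the final analysis.

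A reader might infer that the Week 28 column holds only subjects who declined the extension. It does not: late rollover visits enter it, and many FU1 scores miss it. That corrects the description, but it leaves the column harder to interpret, not easier.

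A reader might also infer that no off-drug within-subject analysis exists anywhere. The documents do not allow that claim, because Protocol 7.3.5.2 and most of SAP 5.3.4 are redacted. The spaghetti plot, the mRSS counts per window by treatment, and the counts entering the extension or follow-up (SAP 5.2.2) let a careful reader see the change in composition. They give no estimate or interval. Protocol 7.3.6.2 does address flares, through summaries or listings of suspected symptoms and adverse events, but not through skin score.

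The size is assumed throughout. Nothing in the documents shows that the choice depends on response, and rollover also depends on regulatory and ethics approval. The 4.0-point maximum needs 80% rollover and a gap of one full SD. It is a within-arm step; equal selection in both arms would leave the between-arm difference undistorted. With so few subjects, a paired between-arm interval will be wide. All of this stands, and it limits the point to a question of display and labelling.

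**Conclusion.** The point holds as an inexpensive improvement to the final-analysis displays. As the plan reads, a step in the mRSS mean line after Week 24 cannot be separated from a change in who was scored. Under assumed rollover of 50–80% and an assumed Week 24 difference of 2–5 points, the within-arm step is 1.0–4.0 points in either direction with no true change, against the protocol's 4-point effect of interest. It is zero if rollover is unrelated to response.

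A reader might go further and infer that the primary Week 24 comparison is biased. The documents do not support that. The readable SAP does not list the visits in the MMRM, and nothing shows that Week 28 is among them. Absence of a paired off-drug mRSS summary is asserted only for the unredacted text.

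**What to change.** - End the by-visit mRSS tables, the mean plots and the responder incidence at any visit after baseline at Week 24. State the visits included in the MMRM.
- Assign FU1 by nominal visit or by days since last dose, not by study day.
- Show FU1 in a separate table and panel marked as off IMP: within-subject change from the last mRSS at or before the end of treatment (Visit 9) to FU1, by arm, in subjects with both scores, with the between-arm difference and 95% CI. Show subjects whose reference score is the ED visit separately, since ED follows discontinuation.
- Set the Week 24 values of these subjects beside those of rollover subjects, so that selection is visible.
- Show late COVID-19 rollover visits apart.
- Label the analysis exploratory. Note that few subjects will contribute, and that pairing reduces the composition artefact but does not remove regression to the mean.

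The cost is SAP wording, one table and one figure panel. No new data are needed.
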